#### Statement of Compliance with Good Clinical Practice

This study will be performed in compliance with the ethical principles of the Declaration of Helsinki and the International Conference on Harmonisation (ICH) Harmonised Tripartite Guideline for Good Clinical Practice (GCP).

# **SYNOPSIS**

Protocol Title: Protocol Number:	A Phase IIa Trial of TLC399 (ProDex) in Subjects with Macular Edema due to Retinal Vein Occlusion (RVO) TLC399A2002	
Investigational Product:	TLC399 (ProDex)	
Study Phase:	IIa	
Primary Objective:	To evaluate the efficacy of different strengths of TLC399 (ProDex) administered as a single intravitreal (IVT) injection in the improvement of visual acuity in subjects with macular edema due to RVO	
Secondary Objectives:	
 
To evaluate the safety and tolerability of different strengths of TLC399 (ProDex) in subjects with macular edema due to RVO
 
To evaluate the efficacy of different strengths of TLC399 (ProDex) for reducing retinal thickness in subjects with macular edema due to RVO
 
	
Overall Study Design: Structure:	Part 1: Multi-center, randomized, double-masked Part 2: Multi-center, randomized, double-masked	
Duration:	Subjects will be evaluated for safety and efficacy for 12 months after the single IVT injection of TLC399 (ProDex). Treatment Period: Single day (Day 1) Follow-up Period: Up to 12 months	
Controls:	Not applicable	
Dosage/Dose Regimen/ Instillation/Application/ Use:	
 
TLC399 (ProDex):
 
Group 1: 0.36 mg dexamethasone sodium phosphate (DSP) with 100 mM phospholipid (PL) (30 μL)
 
Group 2: 0.6 mg DSP with 100 mM PL (50 μL)
 
Group 3: 0.6 mg DSP with 50 mM PL (50 μL)
 
Group 4: 0.84 mg DSP with 50 mM PL (70 μL)
 
In Part 1, subjects will be assigned to Group 1, 2, or 3 (randomized 1:1:1).
 
In Part 2, subjects will be assigned to Group 3 or 4 (randomized 1:1).
 
	

Summary of Visit Schedule:	
 
Visit 1 (Day -14 to Day -1): Screening
 
Visit 2 (Day 1): Eligibility Confirmation and Randomization/Treatment
 
Visits 3-5 (Days 2 [+2 days], 14 [±2 days], 30 [±3 days]) and Visits 6-11 (Day 60 to Day 270 [±7 days]): Follow-up Period
 
Visit 12 (Day 360 [±7]): Exit Visit
 

Measures Taken to Reduce Bias:	Stratified randomization will be used to avoid bias in the assignment of subjects to treatment, to increase the likelihood that known and unknown subject attributes (eg, demographics and baseline characteristics) are evenly balanced across treatment groups, to reduce the possible influence of covariates on the drug evaluation, and to enhance the validity of statistical comparisons across treatment groups. Masked treatment will be used to reduce the potential of bias during data collection and evaluation of clinical endpoints. The subject, the masked Evaluating Investigator (Principal investigator or his/her designees), the best-corrected visual acuity (BCVA) technician, the photographer, and any other site staff involved in performing visit assessments are masked to the study treatment.

# **Study Population Characteristics:**

Number of Subjects:	Part 1: 31 subjects Part 2: Up to 30 subjects
Condition/Disease:	Macular edema due to central retinal vein occlusion (CRVO) or branch retinal vein occlusion (BRVO)
Inclusion Criteria:	
 
Male or female, at least 18 years of age.
 
Subjects with macular edema due to CRVO or BRVO diagnosed within 18 months prior to the Screening Visit with:         
 
Visual acuity decreases attributable to the edema in the study eye; and
 
Non-ischemic type by fluorescein angiography (FA) in the study eye.
 
 
 

	
 
BCVA score of 20/40 (73 letters) to 20/400 (19 letters) by Early Treatment of Diabetic Retinopathy Study (ETDRS) chart in the study eye at the Screening Visit and on Day 1.
 
Mean central subfield thickness (CST) ≥350 µm on spectral domain optical coherence tomography
 

(SD-OCT) measurements in the study eye at the Screening Visit as determined by the site's OCT machine.

- 5. Willing and able to comply with the study procedure and sign a written informed consent.
- 6. Must agree to use a medically acceptable form of birth control throughout the study duration unless the subject or his/her partner(s) is sterile\*.
  \*Sterile is defined as a woman who has experienced menopause (as defined by amenorrhea for greater than 12 consecutive months) or has undergone successful surgical sterilization (hysterectomy, bilateral tubal ligation, or bilateral oophorectomy); or a man who has undergone successful orchiectomy.

Note: If both eyes are eligible for the study, the eye with the shorter duration of disease will be used as the study eye.

- 1. History of diabetic retinopathy in the study eye.
- 2. Presence of a brisk afferent pupillary defect (ie, obvious and unequivocal) in the study eye.
- 3. Stroke or myocardial infarction within 3 months prior to the Screening Visit.
- Poorly controlled hypertension (defined as systolic blood pressure [BP] >160 mm Hg and/or diastolic BP >90 mm Hg) at the Screening Visit or at Day 1.
- Poorly controlled diabetes (defined as hemoglobin A1c level > 9.5%) at the Screening Visit.
- 6. Uncontrolled systemic disease.
- Any ocular condition that in the opinion of the masked Evaluating Investigator would prevent a 15-letter gain in visual acuity in the study eye (eg, severe macular ischemia).
- 8. Presence of an epiretinal membrane in the study eye which, in the opinion of masked Evaluating Investigator, is the primary cause of macular edema, or is severe enough to prevent gain in visual acuity despite reduction in macular edema.
- History of clinically significant (CS) intraocular pressure (IOP) elevation (ie, a rise of ≥10 mm Hg or an absolute IOP ≥ 25 mm Hg which required treatment) in response to topical or systemic steroid treatment in either eye.

**Exclusion Criteria:** 

- 10. History of ocular hypertension, glaucoma, or optic nerve head change consistent with glaucomatous damage in the study eye.
- Active ocular hypertension (with or without treatment) ≥ 22 mm Hg in the study eye at the Screening or Day 1 visit.
- 12. Aphakia or presence of anterior chamber intraocular lens in the study eye.
- 13. Active retinal neovascularization in the study eye.
- 14. Active or history of choroidal neovascularization in the study eye.
- 15. History of central serous chorioretinopathy in either eye.
- 16. Presence of rubeosis iridis in the study eye.
- 17. Any active ocular infection (ie, bacterial, viral, parasitic, or fungal) in either eye at the Screening Visit or on Day 1.
- 18. History of herpetic ocular infection in the study eye or adnexa.
- 19. Presence of active or inactive toxoplasmosis in either eye at the Screening Visit or on Day 1.
- 20. Presence of visible significant scleral thinning or ectasia in the study eye that would preclude safe IVT injection.
- 21. Media opacity in the study eye that precludes clinical and photographic evaluation (including but not limited to preretinal or vitreous hemorrhage, lens opacity).
- 22. Cataract surgery in the study eye within 3 months, or other intraocular surgery in the study eye within 6 months prior to the Screening Visit; or these surgeries are planned during the course of the study.
- 23. Anticipated need for ocular surgery in the study eye during the 12-month study period.
- 24. History of pars plana vitrectomy, radial optic neurotomy, or sheathotomy in the study eye.
- 25. Use of hemodilution for the treatment of RVO within 3 months prior to the Screening Visit.
- 26. Use of IVT ranibizumab or bevacizumab in the study eye within 6 weeks prior to the Screening Visit; or IVT aflibercept in the study eye within 8 weeks prior to the Screening Visit.
- 27. Use of laser of any type in the study eye within 3 months prior to the Screening Visit.
- 28. Previous use of non-depot IVT steroids in the

study eye within 3 months prior to the Screening Visit.

- 29. IVT Ozurdex in the study eye within 6 months prior to the Screening Visit.
- 30. Any prior use of Retisert or Iluvien in the study eye.
- 31. Use of systemic steroids or heparin within 1 month prior to the Screening Visit; or anticipated use at any time during the study.
- 32. Use of immunosuppressants, immunomodulators, antimetabolites, and/or alkylating agents within 6 months prior to the Screening Visit; or anticipated use at any time during the study.
- 33. BCVA score < 34 letters (approximately 20/200 Snellen equivalent) in the non-study eye using the ETDRS chart method at the Screening Visit or at Day 1.
- 34. Known allergy or hypersensitivity to the study medication or its components.
- 35. Known allergy or contraindication to the use of fluorescein or povidone iodine or contraindication to pupil dilation in either eye.
- 36. Female subjects who are pregnant, nursing, or planning a pregnancy.
- 37. Treatment with an investigational drug within 90 days or 5 half-lives of the investigational product ([IP]; whichever is longer) prior to the Day 1 visit.
- 38. Any participation in a clinical trial within 30 days of the Screening Visit.
- 39. Subject has a condition or is in a situation which, in the masked Evaluating Investigator's opinion, will interfere with the subject's ability to comply with the dosing and visit schedules and the protocol evaluations or may not be suitable for this study.

TLC399 (ProDex) is designed as a 2-vial system; 1 with DSP and 1 with PL containing lipid excipients. On Day 1, subjects will be administered a single dose IVT injection according to the randomized group. Mode of Administration: IVT injection to the study eye to be administered by the unmasked Injecting Physician.

#### Primary:

• Proportion of subjects with BCVA gain of 15 or

Study Formulations and Mode of Administration:

**Evaluation Criteria:** Efficacy Measures:

Confidential

more letters from baseline in the study eye at 6 months

# Secondary:

- Change from baseline of retinal CST (using SD-OCT) in the study eye at scheduled visits
- Proportion of subjects with retinal CST (using SD-OCT) <300 µm in the study eye at scheduled visits
- Change from baseline in number of letters read correctly (using BCVA) in the study eye at scheduled visits
- Proportion of subjects with BCVA gain of 15 or more letters from baseline in the study eye at scheduled visits
- Proportion of subjects with BCVA letter score >73 (20/40 Snellen equivalent) in the study eye at scheduled visits
- Time to achieve a treatment response of gain of 15 or more letters from baseline BCVA in the study eye
- Adverse Events (AEs)
- IOP
- Slit lamp biomicroscopy (SLB)
- Indirect ophthalmoscopy (dilated)
- Fundus photography (FP)
- FA
- Physical examination
- Vital signs (BP, pulse)
- Clinical laboratory evaluations (routine hematology, chemistry, and urinalysis)

# **General Statistical Methods and Types of Analyses Sample Size Calculation**

This is an exploratory study and there is no formal sample size evaluation. For Part 1, approximately 20 subjects are expected to be enrolled in each study group completing the 12-month follow-up period after study drug administration. Given a drop-out rate of 10%, approximately 22 subjects in each group will be enrolled. A total of approximately 66 subjects will be randomly assigned to 1 of 3 different strengths of TLC399 (ProDex).

Based on the SMC recommendation, following review of data for 31 subjects from Part 1 (10, 10, and 11 in Groups 1, 2, and 3, respectively), up to 30 additional subjects will be randomly assigned in Part 2 to one of 2 different strengths of TLC399 (ProDex).

# **General Statistical Considerations**

All efficacy and safety variables will be summarized using descriptive statistics and presented by treatment groups. Continuous variables will be presented as number of

# Safety Measures:

TLC399 (ProDex)	Taiwan Liposome Company, Ltd.
Clinical Trial Protocol: TLC399A2002	12 October 2018, v5.0

observations, mean, standard deviation, median, minimum, and maximum, as well as number of missing data (if relevant); while categorical variables will be presented as number of observations, count, percentage, and number of missing data (if relevant) in a frequency table. In general, missing values will remain as missing. Specific rules for handling missing efficacy data are described in Efficacy Analysis.

### **Analysis Population**

The populations for analysis applied in this study are defined as follows:

*Safety population*: All randomized subjects who receive any dose of study drug administration.

*Modified intent-to-treat (mITT) population*: A subset of the safety population comprised of subjects who have at least 1 post-treatment efficacy evaluation. *Per protocol (PP) population*: A subset of the mITT population comprised of subjects who complete the study without any major protocol violations.

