### **Efficacy Analysis**

The efficacy data will be descriptively summarized with the mITT and PP analysis populations and presented by study part and treatment group. Data for the Group 3 dose in both study parts will be pooled and summarized as well.

The mITT analysis will be considered primary and the PP supportive.

For all analyses of BCVA data, missing data will be imputed using multiple imputation methods. Patients who receive rescue medication/procedures within 6 months after the study treatment is initiated will be considered failure to achieve a gain of at least 15 BCVA letters. For continuous measures, all data points after a subject starts rescue medication will be replaced with the last observation prior to rescue medication administration.

Sensitivity analyses on the primary endpoint will be performed as follows:

- 1) On observed data only, with subjects requiring rescue medications prior to Month 6 included as treatment failures (mITT and PP populations)
- 2) Imputing missing data using the last observation carried forward, with subjects requiring rescue medications prior to Month 6 included as treatment failures (mITT population)
- 3) On observed data only, with subjects who require rescue medications prior to Month 6 using their Month 6 data (mITT population)

The same approach to missing data as described for BCVA data will apply to CST data.

The time to achieve a treatment response of gain of 15 or more letters from baseline BCVA will be analyzed using the Kaplan-Meier method. Survival plots will be created and the survival time will be presented as mean, median, 95% confidence intervals (CIs) for the median, and the range.

Change from baseline in number of letters read correctly (using BCVA) and change from baseline of retinal CST (by using SD-OCT scan) in the study eye during the 12-month period will be summarized by treatment groups at scheduled visits. Additionally, 95% CIs for the treatment estimates in changes from baseline will be constructed.

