#### **Interim Analysis**

An interim analysis for the primary efficacy evaluation was planned to be conducted after all subjects have completed at least 6 months in the study or had been withdrawn. For this Phase 2 trial, efficacy and safety evaluation beyond Month 6 will be considered exploratory.

Safety monitoring committee (SMC) reviews will be performed throughout the study. The unmasked SMC reviewed unmasked listings for 31 subjects on 29 March 2018 (data cutoff 09 March 2018), and requested that recruitment be temporarily paused pending further data analysis. Additional descriptive efficacy summaries were provided to the SMC for a review meeting on 25 April 2018. An unmasked team from the sponsor presented further data for an unmasked SMC meeting held on 18 August 2018 (data cutoff 06 August 2018). Following this meeting, the SMC approved the sponsor's proposal to enroll additional subjects treated with the Group 3 dose and a new Group 4 dose (containing a greater volume of the same formulation of Group 3). As of Protocol Amendment 3 (v4), data from Part 1 (31 subjects) will be unmasked. Given that, as of protocol preparation, 1) all 31 subjects randomized in Part 1 have completed at least Month 7.5 in the trial or have been withdrawn (and evaluations beyond 6 months were considered exploratory); 2) no formal statistical comparisons will be made between the groups in Part 1 or Part 2; and 3) the selection of dose to carry forward from Part 1 has already been decided, it was deemed that minimal bias will be introduced by unmasking the data. The sponsor intends to disclose key unmasked efficacy and safety data from Part 1 with the investigators and other stakeholders so that they can adequately understand the benefits and risks of the study treatment.

For Part 2, no formal interim analysis is planned.

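### The per-protocol set requires completion of the 12-month study, so per-protocol analyses of the Month 6 primary endpoint drop subjects whose Month 6 outcome is already known

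*Combined protocol and SAP*

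**What the plan says.** The Analysis Population section of the synopsis defines the PP set as "A subset of the mITT population comprised of subjects who complete the study without any major protocol violations". The mITT set has no completion requirement: it needs only treatment and one efficacy evaluation afterwards.

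The visit schedule ends with "Visit 12 (Day 360 [±7]): Exit Visit", and the Sample Size Calculation text also ties completion to 12 months of follow-up. The primary measure is the proportion gaining 15 letters or "more letters from baseline in the study eye at 6 months". The Interim Analysis section adds: "For this Phase 2 trial, efficacy and safety evaluation beyond Month 6 will be considered exploratory".

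Under Efficacy Analysis, efficacy is summarized in both sets, with these roles: "The mITT analysis will be considered primary and the PP supportive". Sensitivity analysis 1 on the primary endpoint names the PP set explicitly: "On observed data only, with subjects requiring rescue medications prior to Month 6 included as treatment failures (mITT and PP populations".

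On Part 1, the Interim Analysis section states that "all 31 subjects randomized in Part 1 have completed at least Month 7.5 in the trial or have been withdrawn", and "As of Protocol Amendment 3 (v4), data from Part 1 (31 subjects) will be unmasked".

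**The concern.** Membership of the set that supports the Month 6 result is decided by what happens between Month 6 and Day 360. Read plainly, two kinds of subject are lost from the PP analyses of the primary endpoint:

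- subjects with a valid Month 6 BCVA and no major violation who withdraw before Day 360;
- subjects rescued before Month 6, whom the plan already counts as failures, if they later leave. Rescued subjects who stay to Day 360 remain in the PP set as failures.

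Late withdrawal may be related to how well a subject did, so the PP response rate can move either way. The groups hold 10 to 15 subjects, so one exclusion is visible in the displayed percentage.

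There is also a timing problem. The primary efficacy evaluation was planned for when every subject had reached 6 months or withdrawn, but at that point PP status is unsettled for anyone still in follow-up. In Part 1 no Month 6 outcome remained to be collected when the protocol was prepared, yet the PP status of any subject still in follow-up stays open until Day 360, after unmasking.

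**Working it through.** **Inputs from the synopsis.** Part 1 groups of 10, 10 and 11 (31 in total). Part 2 up to 30, randomized 1:1, so up to 15 per group. Group 3 pooled over both parts: 11 + 15 = 26. Both parts: 31 + 30 = 61. Drop-out 10%, stated in the Part 1 sample size text. No timing of drop-out and no response rates are given.

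**The plan's own figure.** 20 completers per group with 10% drop-out: 20 / (1 - 0.10) = 22.2 per group, and 60 / 0.90 = 66.7 in total. The stated figures of about 22 and about 66 reproduce. The 10% is therefore drop-out over the full 12 months.

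**Expected Month 6 outcomes lost through later withdrawal.** Let *s* be the assumed share of drop-out that falls after Month 6, and assume that the 10% also applies to Part 2. Expected loss = N × 0.10 × *s*.

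| Set | N | *s* = 0 | *s* = 0.5 | *s* = 1 |
|---|---|---|---|---|
| Groups 1 and 2, each | 10 | 0 | 0.5 | 1.0 |
| Group 3, Part 1 | 11 | 0 | 0.55 | 1.1 |
| Part 2 group | 15 | 0 | 0.75 | 1.5 |
| Group 3 pooled | 26 | 0 | 1.3 | 2.6 |
| Part 1 | 31 | 0 | 1.55 | 3.1 |
| Both parts | 61 | 0 | 3.05 | 6.1 |

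A constant drop-out hazard is a check on the middle column. The share leaving after Month 6 is then 0.90^0.5 - 0.90 = 0.0487, which gives 31 × 0.0487 = 1.5 and 61 × 0.0487 = 3.0. With 5% or 20% drop-out instead of 10%, the figure for 61 subjects is 1.5 or 5.8.

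These are expected counts, not upper limits; a single group could lose more. They also leave out rescued subjects who withdraw before Month 6, whose failure is known and who are likewise not in the PP set.

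**Effect of one loss.** With r responders among n, the rate becomes r/(n - 1) if a failure leaves and (r - 1)/(n - 1) if a responder leaves. The values of r are assumptions.

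| Start | A failure leaves | A responder leaves |
|---|---|---|
| 3/10 = 30.0% | 3/9 = 33.3% (+3.3) | 2/9 = 22.2% (-7.8) |
| 4/11 = 36.4% | 4/10 = 40.0% (+3.6) | 3/10 = 30.0% (-6.4) |
| 6/15 = 40.0% | 6/14 = 42.9% (+2.9) | 5/14 = 35.7% (-4.3) |
| 10/26 = 38.5% | 10/25 = 40.0% (+1.5) | 9/25 = 36.0% (-2.5) |

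Two losses from a group of 15 give 6/13 = 46.2% (+6.2) if both are failures, or 4/13 = 30.8% (-9.2) if both are responders.

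**The case against.** The strongest reply is that nothing rests on the PP set. The study is exploratory, the mITT analysis is primary, no formal comparisons between groups are made, and the dose carried forward from Part 1 is already chosen. The outcomes are not lost to the report either: a subject who leaves in Month 9 is still in the mITT primary analysis and in all the mITT sensitivity analyses, including the mITT version of sensitivity analysis 1. All of this stands, and it limits the weight of the point. But in a descriptive trial the displayed rates are the result, and a supportive rate should not set aside valid endpoint data because of a later event.

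Second, the supplied text is essentially the synopsis, and a fuller section might define study completion differently. That limits certainty. Still, the visit schedule and the sample size text both point to 12 months, and nothing supplied points elsewhere. If Month 6 was meant, a clarifying sentence is still needed.

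Third, a single completer set keeps the same subjects across all visits, which is a recognizable choice for 12-month summaries. It does not justify requiring six further months of follow-up for an endpoint read at Month 6.

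Fourth, redefining the PP set after unmasking is itself a post hoc change, and a revised set that keeps rescued early leavers as failures while omitting unrescued ones is asymmetric. The first part stands, and disclosure and a second table reduce the risk without removing it. The asymmetry is real, but it follows the plan's own rule in sensitivity analysis 1, which uses observed data and counts early rescue as failure.

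**Conclusion.** The concern holds. As written, the PP analyses of the Month 6 endpoint exclude subjects with a known Month 6 outcome, or a known rescue failure, because they did not reach Day 360. This rests on reading study completion as reaching the Day 360 exit visit, which the supplied text supports and does not contradict.

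At the plan's 10% drop-out, the expected loss through withdrawal after Month 6 runs from 0 to 3.1 of 31 in Part 1, from 0 to 2.6 of 26 in pooled Group 3, and from 0 to 6.1 of 61 overall, depending on the unknown timing. Under the assumed response rates, one loss moves a single-group PP rate by about -8 to +4 percentage points and the pooled Group 3 rate by -2.5 to +1.5. The direction cannot be determined from the documents.

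The mITT result does not change, so this should be corrected but does not threaten the primary analysis.

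**What to change.** For the Month 6 endpoint, define the PP set as mITT subjects who have no major protocol violation up to Month 6 and who either have a Month 6 BCVA or received rescue before Month 6, the latter counted as failures where the plan's failure rule applies. State that withdrawal after Month 6 does not remove a subject from this set. The 12-month completer set can stay for PP summaries of later visits.

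Record that the change was made after Part 1 was unmasked, and show the Part 1 PP results under the present definition as well, so that readers can see whether the choice matters.

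The cost is a second PP definition and one extra Part 1 table; no new data are needed. Two drawbacks remain. For the 31 Part 1 subjects the change comes after unmasking and must be disclosed as such. The revised set also still omits unrescued subjects who leave before Month 6; the mITT analysis with multiple imputation covers them.
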